6.2 Study Participation Discontinuation

The Investigator has the right to discontinue a patient from protocol treatment or withdraw a patient from the study at any time. In addition, patients have the right to voluntarily discontinue protocol treatment or withdraw from the study at any time for any reason.

6.2.1 Discontinuation from Protocol Treatment

Refer to section 5.3.3.

6.2.2 Discontinuation from Study Participation

The primary reason for study participation discontinuation should be documented on the eCRF. Reasons for patient's discontinuation from the study include (but may not be limited to):

- Patient is enrolled but does not receive protocol treatment for any reason
- Patient completes the study
- Death
- Consent withdrawal from entire study participation
- Patient non-compliance
- Lost to follow-up

Should a patient be enrolled, but has never started protocol treatment, she will be discontinued from the trial, and managed according to the site's SoC.

Should a patient decide to withdraw consent, all efforts will be made to complete and report the observations as thoroughly as possible. The Investigator should schedule a visit with the patient, or contact the patient by telephone to establish as completely as possible the reason for the withdrawal. A complete final evaluation at the time of the patient's withdrawal should be made with an explanation of why the patient is withdrawing from the study. After complete withdrawal of consent, no further study procedure is performed and no further data will be collected.

If a patient withdraws consent to the use of study-specific tumor samples:

- The Investigator has the responsibility to notify TRIO immediately.
- TRIO will ensure that the laboratory(ies) holding the samples is/are informed about the withdrawn consent immediately and that samples are either returned to the study site, or disposed of/destroyed by the central laboratory as per site's request/local requirements, and the action documented by the central laboratory(ies).

In the event that analysis/research has already been performed, TRIO or its representatives, in strict compliance with the applicable local regulations, should retain the results and associated data for regulatory reasons but these will not be used in any subsequent analyses. In the case a patient does

not show up for study visits, site staff should make reasonable contact attempts before declaring the patient as lost to follow-up. These attempts need to be documented in the medical records.

6.3 Schedule of Procedures

All study visits and procedures are detailed in the table presented in this section. The detailed description of the study visits and assessments is in sections 6.4 and 6.5.

Table 2: Schedule of Procedures

Protocol Activities	Screening ¹	Treatment Period ²	Pre-surgery ³	BC surgery/pre-NAST biopsy	End of Study ⁴
Informed consent/Registration and Enrollment ⁵	X				
Demographics, medical, surgical, disease history	X				
Complete physical examination ⁶	X		X		
Symptom-directed physical examination		X			X
ECOG PS	X	X	X		X
Weight, height, blood pressure ⁷	X				
Serum pregnancy test	X ⁸				
Hematology, Blood chemistry ⁹	X		X		X
AEs assessments	X	X	X		X
Concomitant medication and therapeutic procedures ¹⁰	X	X	X		X
Treatment compliance assessment ¹¹		X	X		
Tumor sample ¹²	X			X	

Note: All assessments should be performed within 3 days of the scheduled visit, unless otherwise specified.

Footnotes:

1: Screening procedures (except PICF signature and screening tumor samples – see footnote 12) to be done within 28 days of enrollment, unless otherwise specified

2: Protocol treatment should begin within 5 days of enrollment and no more than 42 days after breast tissue collection. Treatment should last at least 14 days, and no more than 35 days (recommended maximum duration 21 days). The need for a clinic visit during this period will depend on the duration of protocol treatment. If duration of treatment with ODM-201 is 14 to 21 days only the Pre-surgery visit needs to be performed after Day 1, unless otherwise clinically indicated. If ODM-201 is taken/expected to be taken for > 21 days (due to planned date of surgery/pre-NAST biopsy, delay in surgery/pre-NAST biopsy, etc.) a visit is required as close as possible to Day 21 +/- 3 days (except in case the pre-surgery visit is planned within Day 21 + / - 3 days).

3: The Pre-surgery visit should be performed the day before BC surgery or the day before BC pre-NAST biopsy is performed. The only exceptions should be:

(a) If for some reason the patient is ordered to stop all oral intakes earlier than the day prior to BC surgery/pre-NAST biopsy, the Pre-surgery visit should be scheduled on the day patient is ordered to stop oral intake; (b) In case the BC surgery/pre-NAST biopsy is planned for a Monday or the day following a holiday; in such cases the Pre-surgery visit should be done on a working day as close as possible to the BC surgery/pre-NAST biopsy (e.g. on a Friday if surgery is scheduled on Monday); or (c) In case that performing Pre-surgery visit on the same day of BC surgery/pre-NAST biopsy is required by site due to logistical reasons or patient's/physician's convenience. Refer to section 6.4.3 for further guidance about the Pre-surgery visit planning and procedures.

4: End of Study visit must be scheduled 30 days (+/- 3 days) after the last intake of darolutamide, even for patients who did not complete the minimum 14 days of protocol treatment. The EoS will be the last study visit for patients. However, for patients experiencing protocol treatment-related AEs/SAEs that are ongoing at the time of the EoS visit, monitoring of these events will continue as clinically indicated until (a) the events have resolved or (b) the events have reached a status which, in the Investigator's opinion, is unlikely to resolve due to the nature of the condition and/or the patient's underlying disease. Frequency of visits will be according to Investigator's judgment.

5: There is no window to obtain the signed and dated PICF. Study-specific screening assessments not considered standard practice by the institution must start only once the PICF has been obtained. Registration takes place as soon as the patient signs the PICF. After screening procedures and if patient meets all eligibility criteria, enrollment will be done according to the process described in section 6.1.2.

6: Complete physical examination will include a complete assessment of body systems (i.e., general appearance, head, eyes, ears, nose, mouth, skin, heart, lungs, lymph nodes, gastrointestinal, genitourinary, skeletal, and neurologic). A complete examination of the breast and regional lymph nodes will also be done.

7: Weight, height and blood pressure must be assessed and collected during screening. Afterwards they will be assessed (as well as other vital signs) according to the SoC.

8: Within 7 days of enrollment, only in WoCBP.

9: Hematology: Hemoglobin, WBC, ANC, platelets. Blood chemistry: AST, ALT, total bilirubin, creatinine.

10: Concomitant medication and procedures include any medication or therapeutic procedure used by the patient within 7 days prior to enrollment until the EoS visit. Refer to section 6.5.4 for the reporting rules in the eCRF.

11: All unused drugs (partially used and empty containers) and the patient diary will be handed over to Investigators at each treatment visit (if any) and at the Pre-surgery visit.

12: Mandatory tissue collection:

- Pre-treatment: A breast tumor sample must be collected at the time of the initial diagnosis (or in a subsequent procedure) either by core needle or incisional biopsy. Excisional biopsy will not be allowed. A minimum of 3 core biopsies using a 14-gauge needle (or the equivalent with an incisional biopsy) is recommended (2 fresh-frozen + 1 paraffin-embedded). In cases it is not possible to provide enough material, collection of 2 cores (or equivalent amount with incisional biopsy) will be acceptable: one core will be snap-frozen and the other one will be prepared in paraffin. For patients who already had such confirmatory biopsy prior to registration, there is no need to repeat it provided that their diagnostic biopsy has been done according to the protocol requirements (in terms of number of cores/tissue, fresh frozen collection, etc.). The screening tumor samples must be collected before start of treatment with darolutamide at the latest.

- BC surgery/pre-NAST biopsy: Two cores (or equivalent amount) of breast tumor tissue must be collected at the time of the patient's surgery or before starting NAST if indicated (1 fresh-frozen + 1 paraffin-embedded).

6.4 Study Visits and Assessments/Investigations

During all visits below, assessments should be done according to the Schedule of Procedures (section 6.3).

6.4.1 Screening Period

The screening period starts with the registration (at time of PICF signature) and ends when the patient is enrolled (following eligibility central review and confirmation by TRIO) or screen failed. When scheduling the screening procedures it should be taken into account that treatment with darolutamide should start within 42 days of the study-specific tumor sample collection.

During the screening period the following assessments will be done:

- Demographics, medical, surgical, disease history
- Complete physical examination (including weight, height and blood pressure measurements)
- ECOG PS
- Serum pregnancy test: only in WoCBP, within 7 days of enrollment (refer to section 4.1 for the definition of WoCBP).
- Laboratory assessments:
 - Hematology: Hemoglobin, WBC, ANC and platelets
 - Blood chemistry: AST, ALT, total bilirubin and creatinine
- Adverse events assessment. For information on the assessment and collection of AEs refer to section 7 and to section 6.3
- Concomitant medications
- Tumor biopsy (refer to section 6.5.7)

Once all screening assessments have been conducted, the site will request enrollment of patients who meet all eligibility criteria through completion of all screening data in RDC (see section 6.1.2.1), and TRIO will review patient's eligibility. No enrollment must take place before formal confirmation of eligibility is provided by TRIO to the site.

Once the patient is enrolled, she will be instructed to begin protocol treatment with darolutamide. If for some reason the patient does not start their study treatment, she will be discontinued from study, and managed as per site's SoC.

If for some reason laboratory tests are repeated between these tests done at screening and treatment start, the most recent measurement obtained prior to treatment start must be within the required values according to the inclusion criteria, to begin protocol treatment.

6.4.2 Treatment Period Visits

Refer to section 5.3.2.1 for timelines regarding protocol treatment.

The need for a clinic visit during this period will depend on the duration of protocol treatment.

If duration of treatment with ODM-201 is 14 to 21 days, only the Pre-surgery visit needs to be performed after Day 1, unless otherwise clinically indicated.

If ODM-201 is taken/expected to be taken for > 21 days (due to planned date of BC surgery/pre-NAST biopsy, delay in BC surgery/pre-NAST biopsy, etc.) a visit is required as close as possible to Day 21 +/- 3 days (except in case the pre-surgery visit is planned within Day 21 + / - 3 days).

During the treatment period visit(s) (if any) the following will be assessed:

- Symptom-directed physical examination
- ECOG PS
- AEs
- Concomitant medication

6.4.3 Pre-surgery Visit

As a general rule, the Pre-surgery visit will be performed the day before BC surgery or the day before pre-NAST biopsy if NAST is indicated.* If after the Pre-surgery visit takes place, the BC surgery/pre-NAST biopsy planned for the following day is delayed for any reason, the Investigator should contact the Medical Monitor to discuss about potential continuation of darolutamide after the Pre-surgery visit.

During this visit the following assessments will be done:

- Complete physical examination
- ECOG PS
- Safety laboratory assessments:
 - Hematology: Hemoglobin, WBC, ANC and platelets
 - Blood chemistry: AST, ALT, total bilirubin and creatinine
- AEs
- Concomitant medication

Other pre-surgical assessments should be done according to the standard of care (SoC) at the site.

The only exceptions to scheduling the Pre-surgery visit on the day prior to BC surgery/pre-NAST biopsy will be in the following cases:

- a. If the patient is ordered to stop all oral intakes earlier than the day prior to BC surgery/pre-NAST biopsy. In such case the Pre-surgery visit should be scheduled on the day patient is ordered to stop oral intake and all test/assessments should be done at that point.
- b. In case the BC surgery/pre-NAST biopsy is planned for a Monday or the day following a holiday and the Pre-surgery visit cannot be scheduled the day prior to BC surgery/pre-NAST biopsy. In such case the following will be done:
 - The Pre-surgery visit should be done on a working day as close as possible to the BC surgery/pre-NAST biopsy (e.g. on a Friday if surgery is scheduled on Monday).
 - The patient will be instructed to continue with darolutamide intakes until the day prior to BC surgery/pre-NAST biopsy or when she is instructed to stop all oral intakes, whichever occurs first.

- c. In case that performing Pre-surgery visit on the same day of BC surgery/pre-NAST biopsy is required by site due to logistical reasons or patient's/physician's convenience. In such case, it is acceptable that Pre-surgery visit is performed on the same day that BC surgery/pre-NAST biopsy takes place, but before any of those procedures are performed. The results from the laboratory safety tests must be available and reviewed by the Investigator before the BC surgery takes place.

**Note: Should they coincide, it is acceptable for the Pre-surgery visit to take place on the day of a treatment period visit (if any). In such cases, assessments should be done according to the Pre-surgery visit requirements.*

6.4.4 BC Surgery/Pre-NAST biopsy

Surgery will be done according to site standards. In patients not receiving NAST, BC tissue will be collected at time of surgery according to section 6.5.7. In patients receiving NAST, a breast tumor sample will be collected during the pre-NAST biopsy (refer to section 6.5.7) after completing darolutamide and before NAST start. As much as possible, sites should avoid scheduling BC surgery/pre-NAST biopsy on Mondays or on the day following a holiday, so that Pre-surgery visit may take place the day prior to BC surgery/pre-NAST biopsy according to section 6.4.3.

In the event that a sentinel lymph node biopsy (SLNB) is performed, periareolar injection is to be conducted. The dye/colloid should not be injected into the tumor itself as this may alter the tissue and affect the molecular analyses to be performed on tumor tissue sample.

6.4.5 End of Study Visit

EoS visit must be scheduled 30 days (+/- 3 days) after the last intake of darolutamide, even for patients who did not complete the minimum 14 days of protocol treatment.

The primary purpose of this visit is to follow-up any AEs/laboratory abnormality ongoing at the time of protocol treatment discontinuation and to assess any new AEs/abnormality that may have occurred since protocol treatment discontinuation. Symptom-directed physical examination, ECOG PS assessment and hematology/blood chemistry should be done at this visit. All AEs will be collected (even if due to neoadjuvant treatment, surgery or adjuvant treatment, regardless of the relationship to darolutamide), as well as relevant concomitant treatment according to rules in section 6.5.4.

EoS will be the last study visit with the exception of patients with protocol treatment-related AEs/SAEs that are ongoing at the time of the EoS visit. In these cases, monitoring of these events will continue as clinically indicated until (a) the events have resolved or (b) the events have reached a status which, in the Investigator's opinion, is unlikely to resolve due to the nature of the condition and/or the patient's underlying disease. Frequency of visits will be according to Investigator's judgment.

6.4.6 Unscheduled Visit Procedures

Unscheduled visits may be performed any time to assess or follow AEs, to perform any clinically-indicated investigation, or at the request of the patient or Investigator.

6.5 Description of Assessments/Investigations

6.5.1 Demographics and Medical History

The Investigator will collect and report in the eCRF demographics and complete history of malignant and clinically-significant non-malignant diseases including known hypersensitivity reactions as well as clinically-significant symptoms.

6.5.2 Physical Examination and Vital Signs

At screening and at the Pre-surgery visit, physical examinations will include a complete assessment of body systems (i.e., general appearance, head, eyes, ears, nose, mouth, skin, heart, lungs, lymph nodes, gastrointestinal, genitourinary, skeletal, and neurologic) per SoC at the study site or as clinically indicated by symptoms. As well, a complete examination of the breast and regional lymph nodes will be done. Weight, height and blood pressure will also be measured at screening, and thereafter according to SoC.

During protocol treatment and EoS visits, a symptom-directed physical examination will be done.

6.5.3 ECOG Performance Status

Assessment of ECOG PS (Appendix 1) is required to assess patient's functional status for study eligibility purposes and will be performed throughout the study according to the section 6.3.

6.5.4 Adverse Events and Concomitant Treatments Assessment

- Adverse events assessment: For information on the assessment and collection of AEs refer to section 7 and to section 6.3.
- Concomitant Treatments: Concomitant treatment includes any medication or therapeutic procedure (e.g. prescription drugs, over-the-counter drugs, herbal/homeopathic remedies, nutritional supplements, blood transfusions, etc.) used by a patient from 7 days prior to enrollment until EoS. The concomitant treatments to be collected and reported in the eCRF are:
 - Any treatment used by the patient within 7 days prior to enrollment
 - After enrollment, only if:
 - Medication is given to treat an AE
 - Medication is listed in sections 5.5.1 or 5.5.2

6.5.5 Laboratory Assessments

At screening:

- Hematology: Hemoglobin, WBC, ANC and platelets
- Blood chemistry: AST, ALT, total bilirubin and creatinine
- Serum pregnancy test: within 7 days of enrollment, only in WoCBP

At the Pre-surgery and EoS visits:

- Hematology: Hemoglobin, WBC, ANC and platelets
- Blood chemistry: AST, ALT, total bilirubin and creatinine

6.5.6 Assessment of Efficacy

No efficacy assessments are planned in this study. With the exception of the examination of breast and regional lymph nodes according to section 6.5.2, disease assessments will be conducted according to the SoC at the study site.

6.5.7 Tumor Tissue Collection and Molecular Evaluation

All tumor samples will be submitted to the study Central Laboratory and will be stored for up to 20 years, unless otherwise required per local regulations, Investigator, IRB/IEC and/or the patient.

Full details on the analyses to be performed on the biologic samples and procedures for sample collection, labeling, storage and shipment/return of biological samples will be described in separate document(s) (e.g. Laboratory Manual, Samples Plan).

6.5.7.1 Breast Tumor Tissue Collection

Collection of the following samples is mandatory in the study:

- **Pre-treatment:** A breast tumor sample must be collected at the time of the initial diagnosis (or in a subsequent procedure) either by core needle or incisional biopsy. Excisional biopsy will not be allowed.

A minimum of 3 core biopsies using a 14-gauge needle (or the equivalent with an incisional biopsy) is recommended to perform the protocol-defined molecular analyses. Once the core biopsies have been removed, two of the cores (or equivalent amount of tumor) must be immediately snap-frozen using the procedure outlined in the study laboratory manual, then stored in liquid nitrogen or at -70 to -80 degrees Celsius at the site. The third sample should be prepared in paraffin according to site's practice. In cases it is not possible to provide enough material, collection of 2 cores (or equivalent amount with incisional biopsy) will be acceptable: one core will be snap-frozen and the other one will be prepared in paraffin.

In patients with multifocal or multicentric tumors, efforts will be made to obtain samples from each discrete lesion.

For patients who already had the confirmatory biopsy prior to registration, there is no need to repeat it provided that their diagnostic biopsy has been done according to the protocol requirements (in terms of number of cores/tissue, fresh frozen collection, etc.).

- **BC surgery/Pre-NAST biopsy:** An amount of BC tissue equivalent to two cores (or 2 cores of tissue) must be collected at the time of the patient's surgery (if no NAST indicated) or at time of the pre-NAST biopsy (if NAST is indicated). The pre-NAST biopsy should be done before NAST start. Half of the tissue will be prepared as fresh-frozen, the other half in paraffin.

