5.3.2 Standard Treatment Schedule

5.3.2.1 Dosage and Administration

Darolutamide will be given at a dose of 600 mg (2 × 300 mg tablets) b.i.d. to a daily dose of 1,200 mg.

The following timelines will be considered for darolutamide administration (refer to Figure 1: Study Schema):

- Darolutamide shall be administered starting within 5 days of enrollment.
- No more than 42 days should elapse from the day the study-specific tumor sample is taken at initial diagnosis (or in a subsequent procedure) to the day of the first intake of darolutamide (*Note: for patients who already had their initial diagnostic biopsy prior to registration and this procedure has been done according to the protocol requirements, the 42- day window should be counted from the date of such biopsy*).
- Minimum duration of treatment will be 14 days prior to BC surgery or to the pre-NAST biopsy (if NAST is indicated) (*Note: a day of treatment is considered as any day where the patient takes any darolutamide intake*)
- A maximum duration of 21 days of treatment is recommended. It is recommended that the date of BC surgery/pre-NAST biopsy is defined prior to starting protocol treatment. The start date of darolutamide (Day 1) will be derived as minus 14 to 21 days from the scheduled BC surgery/pre-NAST biopsy date.
- Treatment will be given until the day prior to the BC surgery, or the day before pre-NAST biopsy or when npo is ordered, whichever occurs first.
- If for some reason BC surgery/pre-NAST biopsy takes place more than 21 days after treatment start, it is acceptable that patient receives darolutamide for more than 21 days and up to a maximum of 35 days; patient should continue protocol treatment until the day prior to BC surgery/pre-NAST biopsy or npo is ordered. In these cases it is strongly recommended to have BC surgery/pre-NAST biopsy done as soon as possible after 21 days of treatment are completed. Also, in any case that treatment is extended beyond 21 days, TRIO Medical Monitor should be contacted to discuss continuation of treatment and the need for assessments.

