8.6 Molecular Analyses

The molecular analyses will be performed on the evaluable population. Descriptive statistics will be used to compare the pre-and post molecular findings.

A correlation analysis between the molecular alterations from the baseline tumor samples and the sample collected following administration of darolutamide, during the definitive BC surgery/pre-NAST biopsy will be conducted.

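### As written, the primary pre/post tissue comparison cannot separate specimen type and elapsed time from the effect of darolutamide

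*Protocol*

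**What the plan says.** **Pre sample.** Protocol 6.5.7.1 requires a sample taken "either by core needle or incisional biopsy. Excisional biopsy will not be allowed". Its frozen part "must be immediately snap-frozen using the procedure outlined in the study laboratory manual".

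**Post sample.** The same section says that "An amount of BC tissue equivalent to two cores (or 2 cores of tissue) must be collected at the time of" surgery or biopsy: it is taken "at the time of the patient's surgery (if no NAST indicated) or at time of the pre-NAST biopsy", half frozen and half in paraffin. Neither this text nor footnote 12 of Table 2 (section 6.3) sets a time to freezing for it.

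**Timing.** Protocol 5.3.2.1 states: "No more than 42 days should elapse from the day the study-specific tumor sample is taken at initial diagnosis" (or at a later procedure) to the first intake. Treatment lasts at least 14 days, with 21 the recommended maximum and 35 the outer limit. Footnote 12 requires only that the pre sample precede treatment.

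**Analysis.** Section 8.6 uses the evaluable population: "Descriptive statistics will be used to compare the pre-and post molecular findings". A correlation analysis of pre and post findings is added. No split or adjustment by specimen type or interval is stated, and section 3.1 describes no untreated group. The positive and negative controls in 6.5.7.2 belong to the experiments; they are not untreated patients.

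**Deferred detail.** Protocol 6.5.7 leaves sample procedures and full analysis details to a Laboratory Manual or Samples Plan. SAP section 1 covers only the secondary objective, and SAP 3.1.3 leaves the molecular analyses to a separate document.

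**The concern.** In patients who go straight to surgery, specimen type changes at the same moment as drug exposure: biopsy before, surgical tissue after. In patients who receive NAST, both samples are biopsies. Elapsed time affects both groups, because part of the interval may pass before any drug is taken.

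A shift common to surgical tissue does not average out over patients. It moves the mean change by the shift times the share of patients with surgical specimens, and a larger sample only makes it look firmer. With no untreated group, a stated comparison by specimen type and interval is the only check available inside the trial, and 8.6 does not ask for one.

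The protocol does guard against one tissue artefact at surgery. On sentinel node mapping, section 6.4.4 says: "The dye/colloid should not be injected into the tumor itself as this may alter the tissue". That sentence concerns dye only, but it shows that tissue artefacts were thought relevant to the molecular results.

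**Working it through.** **1. Permitted interval (Protocol 5.3.2.1; Table 2, footnote 12).** The plan states no pre-to-post interval, so it is built from the windows. Interval = wait before first dose + treatment days, with the post sample on the day after the last dose.

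- Shortest: 0 + 14 = 14 days.
- Longest within the recommended duration: 42 + 21 = 63 days.
- Longest at the outer limit: 42 + 35 = 77 days.

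The 77 is nominal. A 7-day hold, which section 5.4.2 allows, on top of 35 intake days gives 42 + 35 + 7 = 84.

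**2. Drug-free share when the wait is 42 days.**

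| Days on drug | Share before first dose |
|---|---|
| 14 | 42/56 = 75% |
| 21 | 42/63 = 67% |
| 35 | 42/77 = 55% |

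These are permitted extremes, not expected values.

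**3. German version 5.0 (SAP 5.2).** First dose falls within 7 days of diagnosis confirmation and surgery is planned within 21 days of it. If treatment is extended to 35 days, the limit is 7 + 35 = 42 days. This clock starts at the pathology report, not at tissue sampling. The two post-specimen types are the same as in the main protocol.

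**4. How a specimen shift would show.** With no drug effect, apparent mean change = (share surgical) × (shift). Neither input is in the documents. Assume a shift of 0.25 to 0.5 SD of the paired change and a surgical share of 25% to 80%. For illustration only, a nominal two-sided 5% paired t test, simulated at n = 19 (the enrolled HR+/HER2 negative count in SAP 2.3), is positive in:

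| Share surgical | Shift 0.25 SD | Shift 0.5 SD |
|---|---|---|
| 25% | 6% | 8% |
| 50% | 8% | 17% |
| 80% | 13% | 37% |

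The range is thus about 6% to 37%, set almost entirely by assumption. It is lower in the enrolled cohorts of 10 and 7: about 5% to 20% and 5% to 14%.

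**5. Precision of a split.** The 95% half-width for a mean change is t(0.975, n−1)/√n, in SD units.

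- All 36 enrolled: 0.34.
- An even split of 36, 18 per specimen type: 0.50 each.
- A subtype cohort of 8: 0.84.
- That cohort split into 4 and 4: 1.59 each.

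A split across subtypes is workable as description; a split within a subtype is barely informative.

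**6. Would agreement in direction serve as a rule?** Take a true effect of d = 0.5 SD and groups of sizes a and b. P(agree) = Φ(d√a)Φ(d√b) + [1−Φ(d√a)][1−Φ(d√b)]. For 15 and 4: 0.974 × 0.841 + 0.026 × 0.159 = 0.82, so it fails in 18%. For 8 and 2 it fails in 28%, and for 6 and 1 in 35%. With no effect and no shift, the directions agree half the time. A pass/fail rule is therefore unsound.

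**The case against.** The strongest objection is that the relevant documents have not been seen. The Laboratory Manual could set the same freezing time for both samples, and the molecular analysis document could split by specimen type. This stands. A reader might infer that handling and time differences will be read as drug effect; the documents do not support that. They show only that the protocol's own text gives no means of separating them.

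The freezing contrast is also narrow. Footnote 12 of Table 2 uses fresh-frozen and snap-frozen interchangeably for the pre sample, so what is missing for the post sample is the immediacy. It concerns frozen tissue only, and the six markers named in 6.5.7.2 are not tied to frozen tissue. The central laboratory must also find both samples adequate before a patient counts as evaluable, though adequacy is not the same as comparability.

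The analysis is descriptive and meant to generate hypotheses. No test or alpha is stated, so the rates in step 4 describe no planned analysis. A descriptive mean change would still carry the same bias.

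A reader might also infer that all patients are analyzed as one set. Section 8.6 does not say so, and the design is organized by subtype. What can be said is that no split by specimen type is stated.

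Finally, NAST patients are not a clean internal control. They differ from primary-surgery patients in their indication for NAST, and a pre sample may be incisional.

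**Conclusion.** The point holds as a gap in the protocol's text. Two post-specimen types share one time point, the permitted interval runs from 14 to a nominal 77 days with up to 42 drug-free, no untreated group exists, and 8.6 states nothing that would separate these from drug effect. This bears directly on the primary endpoint.

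How large any distortion is cannot be determined from the documents: the surgical share, the artefact size and the actual intervals are not given. The false-positive illustration should not be cited as a finding. The conclusion rests on the protocol and SAP alone and would narrow if the unsupplied documents already standardize freezing or report by specimen type. It is a worthwhile, low-cost improvement, not a flaw that invalidates the study.

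**What to change.** 1. In 8.6 and the molecular analysis document, tabulate each marker's change by post-specimen type (surgical or pre-NAST biopsy), mainly across all subtypes. Show change against drug-free days and on-drug days. Inclusion criterion 8 already needs the pre-sample and first-dose dates, and the diary form records the surgery date.
2. State that a change seen only in surgical specimens, or one that tracks drug-free days, cannot be attributed to darolutamide. Treat agreement between specimen types as supportive only, not as a pass/fail rule.
3. In 6.5.7.1, apply the immediate snap-freezing requirement to the frozen half of the post sample.
4. Reconcile SAP 3.1.3, whose evaluable criteria name surgery only, with Protocol 8.5, which also names the pre-NAST biopsy. Read literally, the SAP wording would leave out the patients needed for the specimen comparison.

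The cost is a few descriptive tables and some sentences of text, with no new patients or procedures. The drawback is imprecise estimates by specimen type, above all within subtype.
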